8.4.3. Electrocardiogram

All by-visit ECG summary tables will present results for Safety Set participants overall, and also by dose level received prior to the evaluation. For summarization of incidence any time post-baseline, participant data will be summarized according to the last dose received when a particular criterion was met (thus, a participant may contribute data under more than one dose if a criterion was met post-baseline while taking different doses). Last value on treatment and last value on study will be summarized under the dose level last received.

The average of any multiple values collected at one visit will be used for summarization of continuous variables, including baseline ECG values. For each ECG measurement (heart rate and PR, QRS, QT, and QTcF intervals), the observed value at each scheduled visit and change from baseline at each scheduled visit will be provided. This summary will also include last values on treatment and on study. Last value on treatment is defined as the last post-baseline value between first dose of IP (exclusive) and up to last dose of IP + 1 day (inclusive). Last value on study is defined as the last post-baseline value after the first dose of IP.

In addition, the number and percentage of participants with PCS and potentially clinically significant change (PCSC) values will be summarized by scheduled timepoint and for any time post-baseline, including last value on treatment and last value on study. Individual values of QTcF will be used for PCS determination rather than the average of multiple values collected at one visit. Potentially clinically significant values will be identified for ECG parameters as outlined in [Table 9](#).

A shift table of overall ECG interpretation from baseline to scheduled post-baseline visits will be presented for the following categories: 'Normal', 'Abnormal, Not Clinically Significant', and 'Abnormal, Clinically Significant'. The shift table will be presented by visit – overall and by dose level.

Clinically significant abnormal findings will be reported as adverse events. The average of any multiple values collected at one visit of each parameter will be included in the data listing.

Table 9: Potentially Clinically Significant Values for QTcF

Units	Criteria for PCS Values (Observed Values)		Criteria for PCSC Values (Change from Baseline)	
	High	Low	Increase	Decrease
msec	>450 msec and \leq 480msec >480 msec and \leq 500msec >500 msec	NA	>30 msec and \leq 60 msec >60 msec	NA

8.4.4. Vital Signs

All by-visit vital sign summary tables will present results for Safety Set participants overall, and also by dose level received prior to the evaluation. For summarization of incidence at any time post-baseline, participant data will be summarized according to the last dose received when a particular criterion was met (thus, a participant may contribute data under more than one dose if a criterion was met post-baseline while taking different doses).

Vital sign results (systolic and diastolic blood pressure [mmHg], pulse pressure (mmHg), body temperature [$^{\circ}$ C], heart rate [beats per minute or bpm], and respiratory rate [breaths per minute]) and changes from baseline will be summarized by scheduled visit – overall and by dose level. Pulse pressure is defined as [systolic blood pressure - diastolic blood pressure].

Potentially clinically significant values will be identified for vital sign parameters as outlined in [Table 10](#). For any post-baseline visit, potentially clinically significant values will be summarized by visit.

Any vital sign results considered clinically significant by the investigator will be captured as adverse events.

Table 10: Potentially Clinically Significant Values for Vital Sign Parameters

Vital Sign	Units	Criteria for PCS Values (Observed values)		Criteria for PCSC values (Change from Baseline values)	
		High	Low	Increase	Decrease
Heart rate (supine and standing)	Beats/min	>120	<40		
Systolic Blood Pressure (supine and standing)	mmHg	>180	<90	≥ 30	≥ 30
Diastolic Blood pressure (supine and standing)	mmHg	>110	<50	≥ 20	≥ 20
Supine - Standing Systolic Blood Pressure	mmHg	≥ 20			
Supine – Standing Diastolic Blood Pressure	mmHg	≥ 10			
Orthostatic hypotension: supine – standing SBP and DBP	mmHg	SBP ≥ 20 and DBP ≥ 10			
		SBP ≥ 20 or DBP ≥ 10			

8.4.5. Physical Examination

The occurrence of a physical examination and the date and time, along with the results of the mental status exam and the abbreviated neurological exam are collected. These will be presented in individual participant data listings only using the Safety Set. After screening, any clinically significant abnormal findings in physical examinations will be reported as AEs.

8.4.6. Columbia Suicide Severity Rating Scale (C-SSRS)

All by-visit C-SSRS summary tables will present results for Safety Set participants overall, and also by dose level received prior to the given visit. For summarization of incidence data any time post-baseline, Safety Set participant data will be summarized according to the dose received immediately prior to the evaluation (thus, a participant may contribute data under more than one dose if a criterion was met post-baseline while taking different doses).

Suicidality data collected on the C-SSRS is collected during the clinic visits at Screening and post-baseline visits. The C-SSRS includes ‘yes’ or ‘no’ responses for assessment of suicidal ideation with numeric rating for the severity (from 1 to 5 with 5 being the most severe) and behavior (from 6 to 10 with 10 being most severe). The “Baseline/Screening” C-SSRS form will be completed at screening (lifetime history and past 24 months). The “Since Last Visit” C-SSRS form will be completed at all subsequent visits.

The categorical outcomes of C-SSRS with binary response (“Yes”/ “No”) include:

Suicidal ideation with 5 being the worst:

- 1: wish to be dead

- 2: non-specific active suicidal thoughts
- 3: active suicidal ideation with any methods (not plan) without intent to act
- 4: active suicidal ideation with some intent to act, without specific plan
- 5: active suicidal ideation with specific plan and intent

Suicidal behavior with 10 being the worst:

- 6: preparatory acts or behavior
- 7: aborted attempt
- 8: interrupted attempt
- 9: actual attempt
- 10: completed suicide

Suicidal behavior is considered worse than suicidal ideation. The participant's non-suicidal self-injurious behavior is also assessed separately as part of C-SSRS:

- 11: self-injurious behavior without suicidal intent

Baseline for each question is defined as the worst of the assessments done before the first dose of IP, excluding the lifetime version. This will typically include the 'past 24-month' version from screening and 'since last visit' version from Day 1, as well as any unscheduled visits done before the first dose of IP; any 'Yes' response will make the baseline value as 'Yes'.

The number and percentage of participants with at least one response of 'Yes' to any C-SSRS suicidal ideation or suicidal behavior item, as well as for participant's non-suicidal self-injurious behavior, will be summarized by visit.

Change from baseline for C-SSRS will be assessed using shift tables. Summary of shift from baseline in C-SSRS suicidal ideation and suicidal behavior will be presented for the categories "no suicidal ideation/behavior", "suicidal ideation", and "suicidal behavior" for each scheduled assessment time point. If the answer to all 5 assessments in suicidal ideation and all 5 assessments in suicidal behavior is 'No', then the category for the table is considered as 'No suicidal ideation/behavior'. If any of the assessments in suicidal behavior are 'Yes', the category is considered as 'Suicidal behavior'. If any of the assessments in suicidal ideation are 'Yes' but all assessments in suicidal behavior are 'No', the category is considered as 'Suicidal ideation'.

In addition, a summary of shift in suicidal ideation from baseline maximum rank score for any time post-baseline maximum rank score will be presented. Maximum score 0 refers to all 'No' for all assessments in the desired period for all 5 questions on suicidal ideation.

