7.4. Dose Adjustment Criteria

If a participant experiences AEs at any time during the Treatment Period that are considered by the investigator to be related to the IP and not tolerable, the investigator may reduce the dose of

IP in 15 mg decrements, including during the initial dose escalation period. Administration of IP will be interrupted for 3 to 8 days before the initiation of the reduced dose.

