12.1.7. Columbia-Suicide Severity Rating Scale (C-SSRS)

Suicidality will be monitored during the study using the C-SSRS ([Posner 2011](#)). This scale consists of a baseline evaluation that assesses the lifetime experience of the participant with suicidal ideation and behavior, and a post-baseline evaluation that focuses on suicidality since the last study visit. The C-SSRS includes 'yes' or 'no' responses for assessment of suicidal ideation and behavior as well as numeric ratings for severity of ideation, if present (from 1 to 5, with 5 being the most severe).

The "Baseline/Screening" C-SSRS form will be completed at Screening (lifetime history and past 24 months). The "Since Last Visit" C-SSRS form will be completed at all subsequent time points outlined in the Schedules of Assessments ([Table 2](#), [Table 3](#), and [Table 4](#)).

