8. STATISTICAL ANALYSIS

8.1. General Considerations

All participant data, including those that are derived, that support the tables and figures will be presented in the participant data listings. Some data may be presented only in participant data listings, some may be presented with a corresponding table or figure; these will be indicated in relevant sections below.

For all safety [REDACTED] analyses where applicable, baseline is defined as the last non-missing measurement prior to the first dose of IP. For scores that are made up of item scores, all item scores must come from the same visit to be considered as baseline for the overall score.

Continuous endpoints will be summarized with n, mean, standard deviation (SD), median, first and third quartiles (Q1, Q3), minimum (min), and maximum (max). The minimum and maximum will be reported with the same number of decimal places as the source (raw) data. Mean and median will be reported to 1 decimal place more than the source (raw) data and standard deviation will be reported to 2 decimal places more than the source (raw) data. Any values that require transformation to standard units (metric or SI) will be converted with the appropriate corresponding precision. In addition, change from baseline values will be calculated at each time point and summarized descriptively.

Categorical endpoints (eg, incidence of an adverse event) will be summarized using counts and percentages. Percentages will be presented to 1 decimal place unless otherwise specified.

Participants will be summarized according to treatment received. “By-visit” summaries are based on the last dose received before the specific evaluation. Adverse events summaries are based on the last dose received before the start of the AE. Note that it is possible for a participant to be counted under more than one dose in summaries. Since baseline is by definition before the first dose of IP, baseline values in listing will have no dose designation, and in summaries it will be presented under “Sage-324 Overall”. For displays for which no such date applies, e.g. demographics, disease history, etc., the presentation will not be by dose group, but will be by aggregate SAGE-324 group.

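### The C-SSRS dose rule credits a 'Since Last Visit' answer to the dose taken just before the visit, so when the dose changes between visits the by-dose columns can place suicidality under the wrong dose

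*SAP*

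**What the plan says.** C-SSRS change from baseline is a secondary endpoint (SAP 4.2) and, like the other safety summaries, is tabulated by dose level and overall (SAP 8.4). Protocol 12.1.7 describes the post-baseline instrument as "a post-baseline evaluation that focuses on suicidality since the last study visit". SAP 8.4.6 says of the 'Since Last Visit' version that the "C-SSRS form will be completed at all subsequent visits".

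For incidence at any time post-baseline, SAP 8.4.6 says "Safety Set participant data will be summarized according to the dose received immediately prior to the evaluation". Its by-visit tables are shown overall and "also by dose level received prior to the given visit". This agrees with SAP 8.1, under which by-visit "summaries are based on the last dose received before the specific evaluation". AEs follow a different rule in the same section: "Adverse events summaries are based on the last dose received before the start of the AE".

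The dose can change between visits. Protocol 7.4 begins "If a participant experiences AEs at any time during the Treatment Period that are considered by the investigator to be related to the IP" and, where such AEs are also not tolerable, permits reduction in 15 mg steps. It adds: "Administration of IP will be interrupted for 3 to 8 days before the initiation of the reduced dose". Visits are weekly to Week 8, then at Weeks 10, 12, 16, 20 and 24, then quarterly (Protocol 7.1). No C-SSRS rule in the visible text of either document uses the date of the ideation or behavior, or the doses taken during the look-back.

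**The concern.** Assigning a result to the last dose before the evaluation suits a laboratory value or an ECG, where finding and evaluation coincide. A look-back questionnaire is different: the event may have happened weeks before the visit, at another dose.

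Take an illustrative record. A participant on 60 mg has ideation in Week 28, stops for the interruption, takes 45 mg from Week 29, and answers 'Yes' at Month 9. The C-SSRS tables count this under 45 mg. If the ideation was also recorded as an AE, the AE tables count it under 60 mg. A reader comparing dose columns would find the report disagreeing with itself, and could misjudge how a secondary safety endpoint relates to dose.

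**Working it through.** The plan states no figure here to reproduce. The check applies the SAP rule to the protocol's visit schedule.

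**Inputs.** Gaps between visits: 7, 14 and 28 days up to Week 24, then about 91 days (Protocol 7.1). The ±2 week windows at both ends (Protocol Table 4) give 91 − 28 = 63 to 91 + 28 = 119 days. Interruption L: 3 to 8 days (Protocol 7.4). Dosing is in the evening. Assumptions not in the documents: the reduction is equally likely on any day of the interval, and visits are in the daytime.

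**Step 1: how often the next form is filed under the lower dose.** Let the last higher dose be on the evening of day t after a visit, and the next visit on day G. The first reduced dose is then on the evening of day t + L + 1. The form goes to the lower dose, although the look-back contains higher-dose nights, when t + L + 1 ≤ G − 1. That leaves G − L − 1 possible days out of G, or none if this is negative.

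| Gap G | L = 3 | L = 8 |
|---|---|---|
| 7 days | 3/7 (43%) | 0/7 (0%) |
| 14 days | 10/14 (71%) | 5/14 (36%) |
| 28 days | 24/28 (86%) | 19/28 (68%) |
| 91 days | 87/91 (96%) | 82/91 (90%) |

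For the 91-day gap, the higher-dose nights reported under the lower dose average (87 + 1)/2 = 44 with L = 3 and (82 + 1)/2 = 41.5 with L = 8. For a 7-day gap there are at most 3.

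**Step 2: continuous version, interruption uniform on 3 to 8 days (mean 5.5).**
- Probability of being on the lower dose at the visit: 1 − 5.5/T. For T = 91 this is 94%; for T = 28, 80%.
- Share of the look-back at the higher dose, given the lower dose at the visit: about (T − 5.5)/(2T). For T = 91 this is 42.75/91 = 47%; for T = 28, 11.25/28 = 40%; for T = 63 and T = 119, 46% and 48%.
- The model is symmetric. At T = 91 the look-back splits into about 47% higher dose, 6% off drug and 47% lower dose.

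**Step 3: the opposite direction.** Titration steps are fixed to study days (Protocol 7.3), while visits have a ±2 day window (Protocol Table 2). At a visit on Day 17 the last dose was 30 mg, on the evening of Day 16. If the previous visit was on Day 8, the look-back holds nine doses: Days 8 to 14 at 15 mg (seven) and Days 15 and 16 at 30 mg (two). The answer is filed under 30 mg. SAP 8.2.6 also provides for unscheduled dose increases, which act in the same direction.

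**Step 4: when no misfiling occurs.** An assessment during the interruption is still filed under the higher dose, correctly for an event at that dose. If the higher dose was last taken before the previous visit, the look-back holds none of it.

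**The case against.** The strongest reply is that the important events are already placed correctly elsewhere. Protocol 7.4 permits a reduction for an AE, so a suicidal event that prompts one is an AE. Its onset date and time are recorded (Protocol 12.2.5), and it is tabulated under the dose before onset in the primary-endpoint tables. This stands. A reader might infer that suicidality disappears from the higher dose in the report, or that up to 100% of triggering events are lost to it. The documents support neither: any misplacement is confined to the by-dose columns of the C-SSRS tables. The reply does not cover a 'Yes' never recorded as an AE, and it leaves the two sets of tables in disagreement.

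A second reply is that the error does not run one way. This also stands, by Step 3. 'Mainly downward' is a fair description for intervals containing a reduction; 'only downward' is not.

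Third, 94% and 47% are conditional on a reduction within a quarterly interval, and assume its timing is unrelated to suicidality. They do not size the total. Visits are weekly through the whole titration, and Exclusion 10 removes people with recent suicidal behavior or positive answers to C-SSRS questions 3 to 5. All of this stands.

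A reader might also take the SAP's remark about a criterion being met while on different doses as proof that the dose at the event was intended. The laboratory, ECG and vital-sign sections carry the same remark, so it is weak evidence of intent for the C-SSRS.

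**Conclusion.** The point holds in limited form. SAP 8.4.6 applies a point-measurement rule to a look-back form. When the dose changes between visits, the by-dose C-SSRS columns can therefore credit an event to a dose the participant was not taking, and can disagree with the AE tables. After a reduction within a 91-day interval, the condition for this is nearly always met (90% to 96% of possible reduction days), and close to half the look-back belongs to the other dose. Both figures rest on the uniform-timing assumption; reading the 47% as a share of events also needs a constant event hazard.

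The consequence is bounded. The summaries are descriptive, and the visible text plans no test between doses. The primary endpoint and the overall column are unaffected, and participant listings allow individual cases to be checked. With neither a reduction rate nor a C-SSRS event rate in the documents, the number of affected records cannot be estimated. The case for correction is that by-dose suicidality should be interpretable and consistent with the AE tables.

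**What to change.** Amend SAP 8.4.6 for 'Yes' answers on 'Since Last Visit' forms, in the by-visit, any-time and shift tables:

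- Where a matching AE is recorded, use the dose at its onset date, consistent with SAP 8.1.
- Where the answer is undated and the look-back spans a dose change, show it in a separate 'dose changed in interval' row, or flag it with both doses.
- Attribute such answers to the highest dose in the interval only as a sensitivity display. As the main rule this would move about as much exposure upward (about 47% at T = 91) as the present rule moves downward, and it would not correct the upward cases in Step 3.
- Leave the overall column as it is.

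The dates are already collected: the dosing diary (Protocol 9.4, listed under SAP Appendix C) and AE onset (Protocol 12.2.5). The cost is a short SAP amendment and some programming to match C-SSRS answers to AE and dosing records, a link the documents do not currently describe. A few events will not belong to a single dose column. The change concerns attribution in the analysis only, not dosing.

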8. SELECTION AND WITHDRAWAL OF PARTICIPANTS

8.1. Participant Inclusion Criteria

Participants are eligible to be included in the study if all of the following criteria are met:

1. Participant has signed an ICF before any study-specific procedures are started.
2. Participant is ambulatory and is 18 to 80 years of age, inclusive, at the time informed consent is obtained.
3. Participant is in good physical health and has no clinically significant findings (excluding ET) that may impact their ability to participate in the study, as determined by the investigator, on physical examination, 12-lead ECG, or clinical laboratory tests.
4. Participant has a clinician-confirmed diagnosis of ET in compliance with all the following criteria:
 - a. Duration of at least 3 years
 - b. Absence of other neurological signs, such as dystonia, ataxia, parkinsonism, task- and position-specific tremors, sudden tremor onset, or evidence of stepwise deterioration of tremor
 - c. Absence of historical or clinical evidence of tremor with psychogenic origin (including, but not limited to, eating disorders and major depression)
5. Participant has completed the planned End of Treatment (EOT) Visit and was not early terminated during the planned Treatment Period in another SAGE-324 study.
6. Female participant agrees to use at least one method of highly effective contraception as listed in Section [9.2.5](#) during participation in the study and for 30 days following the last dose of study drug, unless she is postmenopausal (at least 12 months of spontaneous amenorrhea without an alternative medical cause, with confirmatory follicle stimulating hormone [FSH] >40 mIU/mL), or surgically sterile (bilateral oophorectomy, hysterectomy, and/or bilateral salpingectomy), or does not engage in sexual relations which carry a risk of pregnancy (does include abstinence).
7. Male participant agrees to use an acceptable method of effective contraception for the duration of the study and for 13 weeks after receiving the last dose of study drug, unless the participant does not engage in sexual relation(s) which carry a risk of pregnancy. Acceptable methods of effective contraception are listed in Section [9.2.5](#).
8. Male participant is willing to abstain from sperm donation for the duration of the study and for 13 weeks after receiving the last dose of study drug.

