5. STUDY DESIGN

5.1. Overall Design

This study is an open-label study to evaluate the long-term safety and tolerability of SAGE-324 in participants with Essential Tremor (ET) who have completed the planned End of Treatment (EOT) Visit and who were not early terminated during the planned Treatment Period in another SAGE-324 study. This study includes a Screening Period of up to 28 days, a Treatment Period with weekly outpatient visits for the first 8 weeks, outpatient visits on Weeks 10, 12, 16, 20, and 24, and quarterly outpatient visits thereafter to the end of dosing, and a 14-day Follow-up Period. See the Schedule of Assessments ([Appendix A](#)) for the full list of study assessments and timings. The study is schematically presented in [Figure 1](#).

Participants who have provided informed consent will undergo screening assessments up to 28 days prior to the planned day of dosing. Eligible participants will complete additional eligibility and baseline assessments.

[figure not shown]
Starting on Day 1, participants will self-administer on an outpatient basis a single dose of SAGE-324 once daily in the evening before bed, with a snack if bedtime is not within 2 hours of the evening meal. The dosing will start at 15 mg, and according to the dose escalation schedule provided in Figure 1 below, will be escalated to 60 mg starting on Day 43. If a participant experiences adverse events (AE) at any time during the Treatment Period that are considered by the investigator to be related to the investigational product (IP) and not tolerable, the investigator may reduce the dose of IP in 15 mg decrements, including during the initial dose escalation period. Administration of IP will be interrupted for 3 to 8 days before the initiation of the reduced dose.

During the Treatment Period, participants will return to the study center for safety, tolerability [REDACTED] as specified in [Appendix A](#). In addition, safety phone call study visits will be conducted as deemed appropriate by the investigator to review the current status of the participant. Participants will be trained in the use of software applications and devices necessary to complete questionnaires and/or self-rated study assessments.

The Treatment Period will continue for as long as the participant continues to self-administer SAGE-324 or until marketing authorization, projected to be up to approximately 5 years.

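### The by-visit C-SSRS shift table sets a 24-month worst-case baseline against 'since last visit' windows of 1 to about 15 weeks, so it shows net improvement even with no drug effect

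*SAP*

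**What the plan says.** Change from baseline in C-SSRS responses is a secondary endpoint (SAP 4.2), and SAP 8.4.6 assesses it with shift tables. The baseline rule there is: "Baseline for each question is defined as the worst of the assessments done before the first dose of IP, excluding the lifetime version". The section adds that this will typically combine the 24-month Screening answers with the Day 1 'Since Last Visit' form, and that any 'Yes' makes the baseline 'Yes'. All later visits use the 'Since Last Visit' form, on this schedule: "weekly outpatient visits for the first 8 weeks, outpatient visits on Weeks 10, 12, 16, 20, and 24, and quarterly outpatient visits thereafter" (SAP 5.1).

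Two shift tables are planned:

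- Table 14.3.4.7.2: "Summary of shift from baseline in C-SSRS suicidal ideation and suicidal behavior will be presented for the categories" none, ideation and behavior, "for each scheduled assessment time point".
- Table 14.3.4.7.3: "a summary of shift in suicidal ideation from baseline maximum rank score for any time post-baseline maximum rank score will be presented".

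The number and percentage with any 'Yes' is also summarized by visit without reference to baseline, and C-SSRS data are listed (SAP 8.4.6 and SAP Table 4).

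The general rule in Protocol 13.3 and SAP 8.1 takes the last measurement before dosing as baseline. SAP 6.1 declares no modification from the protocol. Inclusion criterion 5 reads: "Participant has completed the planned End of Treatment (EOT) Visit and was not early terminated during the planned Treatment Period in another SAGE-324 study".

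**The concern.** A shift table is read as change within a person, which requires the same length of look-back on both sides. Here the baseline side covers about 104 weeks and the other side may cover one. Intermittent ideation is far more likely to be caught by the longer window, so participants move from 'ideation' to 'none' for reasons unrelated to SAGE-324. For a CNS-active drug studied without a control arm, a by-visit table that leans toward reassurance is the wrong direction of error.

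Two features add to this. A participant already classed as 'suicidal ideation' at baseline cannot show a worsening in ideation. In addition, all participants come from another SAGE-324 study, and Protocol 7.1 lets laboratory results from that study be reused if taken within 28 days of Day 1. The 24 months will therefore often include that study, and ideation that arose there can become baseline here.

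**Working it through.** The plan gives no expected C-SSRS rate, so there is no figure to reproduce. The check has three parts.

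**1. Windows.** Baseline: 24 months, about 104 weeks. Nominal post-baseline gaps from the schedules of assessments: 1 week to Day 57, 2 weeks to Week 12, 4 weeks to Week 24, about 15 weeks from Week 24 to Month 9 (39 − 24), then about 13 weeks. Ratios: 104/1 = 104; 104/13 = 8; 104/15 ≈ 7.

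**2. Expected shifts with no drug effect.** *Assumptions, not in the documents:* 24-month prevalence p of 2% to 15%; constant risk over time; recurrence from independent (θ = 0) to strongly clustered within person (gamma frailty, θ = 20). N = 750 is the planned size.

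- Independent: P(no ideation in t weeks) = exp(−mt), with m = −ln(1 − p)/104. At p = 5%, m = 0.05129/104 = 0.000493 per week.
- Clustered: P(none in t) = (1 + θmt)^(−1/θ), with m = [(1 − p)^(−θ) − 1]/(104θ). At p = 5% and θ = 20, m = 1.7895/2080 = 0.000860.
- Net apparent improvement = 750 × [p − P(Yes in t)].

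At p = 5%, baseline 'Yes' = 37.5:

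| Post-baseline window | 'Yes' in window (θ = 0; θ = 20) | Net apparent improvement (θ = 0; θ = 20) |
|---|---|---|
| 1 week | 0.4; 0.6 | 37.1; 36.9 |
| 13 weeks | 4.8; 7.5 | 32.7; 30.0 |
| 15 weeks | 5.5; 8.6 | 32.0; 28.9 |
| 24 months, cumulative | 37.5; 37.5 | 0; 0 |
| 60 months, cumulative | 90.3; 61.1 | −52.8; −23.6 |

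The first three rows describe Table 14.3.4.7.2. The last two describe the overall column of Table 14.3.4.7.3, whose window grows with time on study. At 13 weeks the net figure is 12.7 to 13.1 for p = 2% and 61.4 to 97.4 for p = 15%.

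The share of on-treatment 'Yes' that falls in baseline-'Yes' participants, and so is not shown as a worsening, is [1 − S(104) − S(t) + S(104 + t)]/[1 − S(t)], where S(t) = P(none in t). At 13 weeks and p = 5% this is 5% (θ = 0), 26% (θ = 5) and 64% (θ = 20).

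**3. Which changes each table can show.** Exclusion 10 removes suicidal behavior within 2 years and any 'Yes' to questions 3 to 5 at Screening or Day 1. An eligible baseline is therefore ideation rank 0, 1 or 2 with no behavior.

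- By visit, three categories: baseline rank 1 or 2 with on-treatment rank 1 to 5 stays in 'ideation'. Even 2 to 5 shows no shift.
- Any-time rank: 1 to 2–5 and 2 to 3–5 show as worsening. Only 1 to 1, 2 to 1 and 2 to 2 do not.
- New suicidal behavior always changes category in the by-visit table.

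**The case against.** The strongest reply is that recurrence is not lost. By-visit counts of any 'Yes' take no account of baseline, listings give the individual answers, new behavior always appears as a shift, and the any-time table shows every rise in rank. This stands. What is missing is recurrence shown as a worsening in the by-visit change-from-baseline display.

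A reader might infer that both shift tables are biased toward reassurance. The documents do not support that. Table 14.3.4.7.3 uses the maximum over all post-baseline time: its windows balance at 24 months on study and its overall column leans toward apparent worsening after that. Its dose columns are less secure. For participants titrating on schedule, the 15, 30 and 45 mg steps last 14 days each, so those columns would set 104 weeks against about 2.

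A reader might also infer that every participant's baseline contains ideation from SAGE-324 exposure. That is not documented either. No maximum gap from the parent study is stated, the laboratory reuse is optional, and completing a parent study does not mean having received SAGE-324; 324-ETD-201, for example, was placebo-controlled.

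A Day 1 baseline has its own bias. It looks back at most about 28 days, so in the any-time table it would create the opposite mismatch. At p = 5%, about 1.5 to 2.5 participants would be 'Yes' at baseline, against 37.5 over 24 months on study. This argues for adding a table, not for replacing the baseline everywhere.

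Finally, the specific rule in SAP 8.4.6 can be read as overriding the general one in SAP 8.1. That settles which rule the programmer follows, but not why SAP 6.1 reports no change from Protocol 13.3.

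**Conclusion.** The concern holds for Table 14.3.4.7.2. Its baseline and post-baseline windows differ by a factor of about 7 to 104, so it shows net improvement in a population with constant risk, and it cannot show worsening of ideation in anyone with baseline ideation. The direction does not depend on the assumed prevalence; the size does. At an assumed 5% prevalence it is about 37 of 750 at 1-week visits and 30 to 33 at 13-week visits. The amount of masking depends on how strongly ideation clusters within people, from 5% to 64% of on-treatment 'Yes' at 13 weeks under the same prevalence. The true number cannot be found from the documents.

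Overlap of the 24 months with parent-study SAGE-324 exposure is likely for many participants but not certain for any given one. The departure from the protocol's last-measurement baseline is a separate, documented inconsistency that SAP 6.1 should record. The displays are descriptive, so the consequence is a misleading table rather than a wrong test.

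**What to change.** - Keep the 24-month baseline for Table 14.3.4.7.3.
- Keep Table 14.3.4.7.2 and add a version with the predose Day 1 'Since Last Visit' form as baseline, showing ideation by rank 0 to 5 and behavior separately. Under the 5% illustration, net apparent improvement at a 1-week visit falls from about 37 to between 1 and 2. At 13 weeks it becomes a slight apparent worsening of 3 to 5.
- Report post-baseline 'Yes' separately by 24-month status and by Day 1 status, flagging participants previously exposed to SAGE-324. Protocol 10.6 already requires these participants to be identified in the safety database.
- Declare the C-SSRS baseline in SAP 6.1 as a departure from Protocol 13.3, with the reason.

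The cost is SAP wording, one extra table and one split, all from data already scheduled. The downside is that the short Day 1 look-back will count some intermittent pre-existing ideation as emergent, which is why the 24-month version should stay beside it.
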